**3. How many subjects will be enrolled at all sites?**

**INSTRUCTIONS:** This number must be the same or higher than the # from question # 1 in order to account for the # of screen failures, dropouts, withdrawals described in question # 2.

**Answer/Response:**

60

**4. How many subjects will sign a consent form under this UVA protocol?**

**INSTRUCTIONS:** If the protocol does not have a consent form- the number listed here should reflect such things as the number of subjects from whom specimens will be obtained, the number of charts to be reviewed etc.

**Answer/Response:** 60

## Inclusion/Exclusion Criteria

**INSTRUCTIONS:**

- The inclusion and exclusion criteria should be written in bullet format.
- *This item applicable if the study will require consent (verbal or written).* Unless there is a scientific reason for not recruiting a certain type of vulnerable population(e.g. not enrolling fetuses, neonates or children in a study regarding Alzheimer's) list the following vulnerable populations under either Inclusion or Exclusion criteria below: pregnant women, fetuses, neonates, children, prisoners, cognitively impaired, educational or economically disadvantage, non- English speaking subjects .
- If you will not enroll subjects who do not speak English because certain procedures cannot be carried out if the subject does not speak English (e.g. a survey is not validated in other languages) insert the following as an Inclusion Criteria: Willingness and ability to comply with scheduled visits and study procedures.
- If this is a collection of only retrospective\* specimens or data, the inclusion criteria must include a start and stop date for when specimens/ data will be collected.
- The stop date must be prior to the version date of this protocol.

- \*Retrospective: all specimens are in a lab at the time this protocol is approved by the IRB. All data exists in medical records or records from previous studies at the time this protocol is approved by the IRB.

### 1. List the criteria for inclusion

Answer/Response:

- 65 years old or older
- A (previous) JABA center user
- Able to walk unassisted for up to 20 minutes
- Willing to comply with COVID-19 regulations

### 2. List the criteria for exclusion

Answer/Response:

- Under 65 years
- Never used a JABA center
- Unable to walk unassisted for up to 20 minutes
- Unwilling to comply with COVID-19 regulations

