### Answer/Response:

Building on pilot work from our team exploring green space activity type, this study aims to focus specifically on older adults in Charlottesville and the surrounding areas. We aim to understand how green space activity type may influence belonging, loneliness and mood and how this may impact on willingness to return to JABA centers. Our research questions are as follows;

1. What types of green space activities have a beneficial impact on loneliness, belonging and mood in seniors who are JABA center members?
2. Does the inclusion of these activities encourage JABA service users to continue participation at their JABA centers?

To investigate these questions, we will utilize 2 study components. The first, titled 'activity sessions' refers to a participant group who will undergo a series of activities (on separate days) including walking, citizen science and planting in order to understand pre- and post-activity wellbeing. The second component, titled 'survey-only', refers to a different participant group who are remotely surveyed on their current wellbeing, experiences during COVID and barriers on returning to JABA. All participants will be JABA service users.

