**2. What are the statistical considerations for the protocol?**

The objectives section and the statistical section should correspond, and any objective for which analysis is unfeasible should be deleted. Also, the estimates and non-statistical assumptions of the statistical section should be supported by discussion in the background section.

The answer to this question should include:

- Study Design/Endpoints
- Recap of study objectives and endpoint definitions. An assessment of how study objectives will be assessed by identifying & defining which endpoints will be used to assess each component of the study objectives.
- The study design should include contingencies for early stopping, interim analyses, stratification factors (if applicable), and any characteristics to be incorporated in analyses.
- The power/precision of the study to address the major study endpoint(s), the assumptions involved in the determination of power/precision.
- If statistical hypothesis testing is included then specify the null and alternative hypotheses, the test statistic, and the type I and II error rates
- If precision of an estimate, then provide a definition for precision
- If other, then specify

Answer/Response:

This is a pilot study aimed at ascertaining impacts of outdoor activities on both wellbeing as well as understanding barriers to returning to JABA centers.

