**Answer/Response:**

There are two components to this study, so we describe each separately. *Activity sessions*

There will be three activity sessions, the protocol for each is largely the same. For the walking and the citizen science sessions, participants will be transported (Jaunt bus) to a nature preserve to conduct this session. Alternatively, if participants wish to transport themselves, they are welcome to – this will be confirmed after obtaining consent. The planting session is held at the JABA center. Upon arrival at the given site, participants will be given their initial pre-activity survey to complete (pen and paper) and are given an accelerometer to wear throughout the study session. Following this, they will undertake their activity; this will include a short nature walk, a guided citizen science walk or a session planting and tending to greenery in raised beds. At the end of the sessions (up to 30 minutes), participants will complete the post-activity survey and remove their accelerometer. After payment (\$10 supermarket voucher per session), participation ends.

*Survey Only*

Participants are mailed a study information sheet and the the survey with a return envelope. They are asked to complete the survey and return it to the research team.

**1. If this protocol involves study treatment, explain how a subject will be transitioned from study treatment when they have completed their participation in the study.**

**Example:** If the subject will be taking an investigational drug, will they need to be put back on an approved drug when they have completed the study? If yes, explain how this will be accomplished and who will cover the cost. If the subject has a device implanted will it be removed? Again- who will cover the cost of the removal?

**Instructions:** Answer NA if this study does not involve a study treatment.

**Answer/Response:** N/A

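### The walking criterion also applies to the mailed survey-only group, so the component that asks about barriers to returning leaves out users with limited mobility

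*Combined protocol and SAP*

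**What the plan says.** Inclusion/Exclusion Criteria, questions 1 and 2, give a single inclusion list and a single exclusion list. Inclusion requires a user to be "Able to walk unassisted for up to 20 minutes". The exclusion list repeats this in the negative, "Unable to walk unassisted for up to 20 minutes", and adds "Unwilling to comply with COVID-19 regulations". Neither list is divided by component, and no other section waives a criterion for one of the groups. The only other statement about the population of both components is in Objectives/Hypothesis: "All participants will be JABA service users".

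Objectives/Hypothesis describes the survey-only component as a separate group "who are remotely surveyed on their current wellbeing, experiences during COVID and barriers on returning to JABA". Statistical Considerations, question 2, names "understanding barriers to returning to JABA centers" as one of the purposes of the pilot. Under Study Procedures, question 1, the survey-only procedure is entirely postal: "Participants are mailed a study information sheet", together with the survey and a return envelope.

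The survey-only group has a second role. Study Design, question 1, makes it the second control, and Statistical Considerations, question 4, compares it with the activity group by an independent t-test on the measures taken in both.

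**The concern.** The walking criterion has an evident purpose in the activity sessions, two of which are walks at a nature preserve. It has no such purpose for a form filled in at home. In the survey it acts only as a selection rule, and it selects on something that is itself a plausible reason for not coming back to a center.

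The Background says JABA estimates that only about a third of its service users have returned since the September reopening, and the inclusion list admits previous users. People who have stayed away are therefore within the intended reach of the survey. Leaving out those with limited mobility means the survey cannot show how much mobility contributes. This is a selection bias, so recruiting more people under the same criteria would not reduce it. JABA could read the result as evidence that mobility is a minor obstacle when the people affected were never asked.

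**Working it through.** **Sample size in the plan.** The Subjects section gives 60 enrolled and about 10% attrition. 60 × (1 − 0.10) = 54, and 54 / 2 = 27 per group. The stated figures reproduce. The sample size is justified by feasibility alone (Statistical Considerations, question 3), so there is no power target to check.

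**Criteria against procedures.**
- Walking ability: needed for the activity sessions; not needed for a mailed survey.
- Willingness to follow COVID-19 regulations: relevant to group attendance; the survey-only procedure involves no attendance.
- Question on barriers to returning: assigned to the survey-only component.

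The documents give no reason for applying either criterion to the mailed group.

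**Worst-case illustration (assumed inputs).** Let q be the true prevalence of a barrier among all users and p the share of users the criteria exclude. If every excluded person has the barrier, observed prevalence = (q − p) / (1 − p). With q = 0.40:
- p = 0.10: 0.30 / 0.90 = 0.333
- p = 0.20: 0.20 / 0.80 = 0.250
- p = 0.30: 0.10 / 0.70 = 0.143

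**Softer illustration (also assumed).** Let b0 be the prevalence among eligible users and b1 among excluded users. The true prevalence is (1 − p)·b0 + p·b1, and the survey sees only b0. With p = 0.20, b0 = 0.10 and b1 = 0.60, the true value is 0.08 + 0.12 = 0.20 against 0.10 observed. For p from 0.10 to 0.40 and (b0, b1) of (0.10, 0.60), (0.10, 0.90) or (0.20, 0.80), the shortfall runs from 5 points (0.15 against 0.10) to 32 points (0.42 against 0.10).

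**Sampling error for scale.** At n = 27 the 95% half-width is 1.96 × √(π(1 − π)/27), where π is the prevalence being estimated. This gives 11.3 points at π = 0.10, 15.1 at 0.20 and 18.9 at 0.50. The bias may be smaller or larger than this, but unlike sampling error it does not shrink as n grows.

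**Cost of widening the survey.** Assume 27 survey respondents who mirror all users, with only those meeting both criteria entering the t-test:
- p = 0.10: 27 × 0.90 = 24.3, about 24
- p = 0.20: 27 × 0.80 = 21.6, about 22
- p = 0.30: 27 × 0.70 = 18.9, about 19

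With equal standard deviations and m in the comparator, the standard error of the group difference changes by the factor √[(1/27 + 1/m) / (2/27)]. This is 1.03 at m = 24, 1.06 at m = 22 and 1.10 at m = 19.

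**The case against.** The strongest defense is comparability. The survey-only group is a control, allocation is not randomized (Statistical Considerations, question 1), and the planned t-test is unadjusted. A shared walking criterion is one of the few features that make the groups alike. This has force, although the protocol does not offer it as a reason and shared criteria alone would not make non-randomized groups comparable. It supports applying the criterion within the t-test. It does not support applying it to the barrier questions, and the two uses can be separated.

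It can also be said that barriers are exploratory here. Neither numbered research question asks about them directly, and the outcome list in Statistical Considerations, question 4, contains no barrier measure or analysis. That limits the weight of the point, but understanding barriers remains a declared purpose of the pilot.

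Three stronger readings are tempting, and the documents do not support them.
- A reader might infer that the plan removes those most likely to have COVID-related barriers. The criterion removes only people unwilling to follow the regulations. Someone who stays away from fear of infection or because they are shielding may be fully willing to comply, and so remains eligible.
- A reader might take the 33%, 25% and 14% as estimates. Both the 40% and the assumption that every excluded person has the barrier are invented for illustration. Even on those terms the smallest shift, about 7 points, is within sampling error at n = 27.
- A reader might assume the exclusion is certain to operate in practice. Study Procedures describes no eligibility screening for mailed participants. If the criteria are not enforced, the survey would enroll people the protocol excludes, and the t-test would compare groups that differ in mobility with no record of it. Either way the text needs repair.

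**Conclusion.** The point holds, chiefly for mobility. Followed as written, the plan excludes people who fail the walking criterion from a postal survey that needs no walking and that asks about barriers to returning. Mobility-related barriers will be under-represented, provided they are more common among excluded than eligible users. That is a reasonable inference, though not something the documents state. The COVID-compliance criterion adds a narrower version of the same problem.

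The size cannot be derived from the documents. The worst-case figures show that the effect could be large. The softer assumptions give a shortfall of anything from 5 to 32 points. This does not undermine the activity-session comparisons. It limits what can be concluded about barriers, and it should be settled before the surveys are mailed.

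**What to change.** State eligibility separately for each component. Apply the walking and COVID-compliance criteria to the activity sessions only, and keep age and JABA use for both. Add two items to the mailed survey: whether the respondent meets the walking criterion, and whether they are willing to follow COVID-19 regulations. Report barriers on all survey respondents. Restrict the activity versus survey-only t-test to survey respondents who meet both criteria.

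The cost is a change of eligibility wording, two questions, and some precision in the group comparison. With enrollment fixed at 60, the comparator could fall to the sizes worked out above, with a standard error up to about 10% larger. That is tolerable in a pilot with no stated power target.

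If the sponsor prefers to keep the shared criteria, the protocol should give the reason and limit its barrier conclusions to users who are mobile and willing to comply. That alternative costs only wording, but it leaves the barriers of less mobile users unexamined.

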### 3. List any restrictions on use of other drugs or treatments.

**INSTRUCTIONS:** List only those drugs or treatments that are prohibited while on study, not those listed as an exclusion criteria.

Answer/Response:

None

## Statistical Considerations

### 1. Is stratification/randomization involved?

Answer/Response: No

#### ► IF YES, describe the stratification/ randomization scheme.

**INSTRUCTIONS:**

The stratification factors and/or the randomization plan should be identified. If there is no randomization component or important patient characteristics that will be used in treatment allocation or data analysis, a statement to this effect should be included.

Stratification factors: These are pretreatment patient characteristics which could be balanced across treatment arms by design or may be used to determine starting dose or treatment allocation.

If randomization is going to be used, the details of the randomization plan should be described.

The description should include:

--the method and timing of randomization

- the type of randomization scheme that will be used in the study
- whether or not the randomization masked/blinded/if so, then to whom is it masked/blinded
- who has access to the randomization scheme

Answer/Response: N/A

► IF YES, who will generate the randomization scheme?

- Sponsor
- UVA Statistician. Insert name Answer/Response:
- UVA Investigational Drug Service (IDS)
- Other: Specify Answer/Response:

**2. What are the statistical considerations for the protocol?**

The objectives section and the statistical section should correspond, and any objective for which analysis is unfeasible should be deleted. Also, the estimates and non-statistical assumptions of the statistical section should be supported by discussion in the background section.

The answer to this question should include:

- Study Design/Endpoints
- Recap of study objectives and endpoint definitions. An assessment of how study objectives will be assessed by identifying & defining which endpoints will be used to assess each component of the study objectives.
- The study design should include contingencies for early stopping, interim analyses, stratification factors (if applicable), and any characteristics to be incorporated in analyses.
- The power/precision of the study to address the major study endpoint(s), the assumptions involved in the determination of power/precision.
- If statistical hypothesis testing is included then specify the null and alternative hypotheses, the test statistic, and the type I and II error rates
- If precision of an estimate, then provide a definition for precision
- If other, then specify

Answer/Response:

This is a pilot study aimed at ascertaining impacts of outdoor activities on both wellbeing as well as understanding barriers to returning to JABA centers.

**3. Provide a justification for the sample size used in this protocol.**

Include sample size calculations or statistical power estimation. If not applicable, please provide explanation.

Also include the anticipated accrual rate, the accrual goal for the study, including accrual goals by strata if appropriate, adjustments for drop-outs etc. and study duration.

Answer/Response: In collaboration with JABA, an n of 60 across the two study components is a realistic number of participants to be able to recruit.

**4. What is your plan for primary variable analysis?**

UVA Study Tracking: HSR210100

Version Date: 03-22-21

Page Number: 6 of 11

Include primary outcome(s)/predictor variable(s), statistical methods/models/tests to be employed, or descriptive summaries as appropriate. If not applicable, please provide explanation.

**Answer/Response:** We will use the following outcome measures across the study.

- Loneliness; measured by the UCLA Loneliness Scale, a 3-item scale that captures feelings of loneliness. (Activities and survey-only)
- Belonging; measured by the General Belonging Scale (GBS), a 12-item scale capturing social acceptance/inclusion and social rejection/exclusion. (Activities and survey-only)
- Acute Mood; pre and post measures of mood will be taken using the UWIST Mood Adjective Checklist (MACL), an acute measure of hedonic tone, stress and arousal. (Activities only)
- Restoration; Psychological restorative qualities of the setting measured by the Perceived Restorativeness Scale, a three point scale determining the restorative quality of activity spaces. (Activities only)
- Physical Activity; In addition to the arousal measure of the MACL, we will use the 10 point scale of the OMNI Perceived Exertion scale, to understand how physically exerted participants feel between activities. To understand baseline physical activity, we use the international physical activity questionnaire (IPAQ) to compare between studies (Activities and survey-only).
- Accelerometer; we will use accelerometers to measure participant movement throughout the activities to correlate with physical activity measures. (Activities only). Specifically, we will look to understand if increased movement, as measured by the accelerometer, correlates with increased feelings of exertion post-activity (across all three activities).

For measures taken in both the activities and survey-only, we will use an independent t-test using condition (activity or survey) to compare. For activities that use pre- and post-assessments, we will make change scores for each and use this in a one-way ANOVA, using activity type (three levels; walking, citizen science, planting) as the grouping variable.

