## Study Design: Biomedical

### 1. Will controls be used?

Answer/Response: Yes

► IF YES, explain the kind of controls to be used.

Answer/Response: There are two controls. First, during the activity sessions, participants will act as their own control, crossing over to take part in each activity. Second, we also will conduct a survey remotely in which participants will respond to questions regarding their current wellbeing. These will be compared to those of the participants who undergo the activity sessions.

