### 2. What is the study design?

Example: case series, case control study, cohort study, randomized control study, single-blind, double-blind, met-analysis, systematic reviews, other. You may also view the IRB-HSR Learning Shot on this topic to help you answer this question.

[https://hrpp.irb.virginia.edu/learningshots/Writing\\_protocol\\_June09/player.html](https://hrpp.irb.virginia.edu/learningshots/Writing_protocol_June09/player.html)

Answer/Response: For the activity sessions, the study is a repeated measures study design. For the survey only group, the study is a single cohort study.

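### The survey-only group is called a control but differs from the activity group by more than activity, so the planned unadjusted t-test, on an unspecified activity score, cannot isolate an activity effect

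*Combined protocol and SAP*

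**What the plan says.** Study Design: Biomedical, question 1, states: "There are two controls". The first is each activity participant as their own control across the three activities. The second is the remotely surveyed group, of whose wellbeing answers it says: "These will be compared to those of the participants who undergo the activity sessions". Question 2 of the same section describes that group differently: "For the survey only group, the study is a single cohort study".

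Objectives/Hypothesis says that survey-only "refers to a different participant group who are remotely surveyed on their current wellbeing". Its first research question is: "What types of green space activities have a beneficial impact on loneliness, belonging and mood in seniors who are JABA center members"? Statistical Considerations, question 1, answers that there is no stratification or randomisation. Question 2 calls the study a pilot "aimed at ascertaining impacts of outdoor activities on both wellbeing" and barriers to returning.

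Statistical Considerations, question 4, lists loneliness (3 items), belonging (12 items) and the IPAQ as taken in both components. It then says: "For measures taken in both the activities and survey-only, we will use an independent t-test using condition (activity or survey) to compare". No covariate, matching or time point is named. Mood is the only scale said to be taken both before and after an activity. A separate sentence puts change scores, wherever pre and post assessments exist, into a one-way ANOVA by activity type.

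Study Procedures gives activity participants a paper survey on arrival and another at the end of each of three sessions. Survey-only participants return one mailed survey. The contents of these surveys are not listed.

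**The concern.** A control is there to show what would have happened without the activity. This group can do that only if it resembles the activity group in everything else that bears on loneliness and belonging, and nothing in the design secures this. The members are different people, allocation is not random, and the test adjusts for nothing. Setting and timing differ too: on site around a session for one group, by post for the other. Both surveys appear to be on paper, so the difference is not one of mode.

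Willingness to come out to a session could itself be related to loneliness or belonging. If so, a difference in who attends could be read as an activity effect, or could hide one. Because the activity score is unspecified, the quantity being estimated is also undefined.

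**Working it through.** **1. The plan's own figure.** Subjects, question 2, expects 10% attrition from 60: 60 × 0.90 = 54, and 54 / 2 = 27 per group. This reproduces. The plan gives no SD, effect size, alpha or power, so what follows is in SD units with an assumed two-sided 5% level and equal SDs.

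**2. What the contrast contains.** Write the expected difference in means as *a* + *s* + *m*, where *a* is the activity effect, *s* the prior difference between the two samples and *m* the effect of survey setting. The t-test estimates the sum. No planned analysis separates the terms.

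**3. Which score enters.** If the scales are in every session survey, each activity participant has up to 3 sessions × 2 surveys = 6 candidate scores, against 1 mailed score.

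| Activity score used | What the difference contains |
|---|---|
| Before the first session | *s* + *m*; no activity effect |
| Before a later session | *s* + *m*, plus any carry-over from earlier sessions |
| After a session | *a* + *s* + *m*, mixed |

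These are different quantities, and the plan does not choose among them.

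**4. Precision at 27 v 27, one score per person.** Half-width = t(0.975, 52) × √(2/27) = 2.007 × 0.272 = 0.546 SD.

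**5. Illustration of the bias.** Let *b* = *s* + *m*, and suppose a post-session score is used and the interval is read as an estimate of *a*. Coverage of *a* is 1 minus the two-sided rejection probability of a noncentral t with 52 df and noncentrality *b* × √(27/2). It does not depend on *a*.

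| Assumed *b* (SD) | Rejection probability at *b* | Coverage of *a* |
|---|---|---|
| 0.2 | 0.111 | 0.889 |
| 0.3 | 0.191 | 0.809 |
| 0.5 | 0.438 | 0.562 |

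Simulation with *a* = 0.5 SD (100,000 runs for each *b*) gave the same three coverage values. The documents support no particular *b*.

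**6. Within-person change, for scale.** In 27 people at one session, half-width = t(0.975, 26) × √(2(1 − r)/27). With an assumed pre/post correlation r of 0.5, 0.7 or 0.8 this is 0.396, 0.306 or 0.250 SD. Such a change contains no *s*, because each person is compared with themselves. It still contains anything else that alters between the two surveys.

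**The case against.** **The plan never says that a group difference will be credited to the activities.** This is true. The test sentence only says that the groups will be compared, the word control answers a form question, and the first research question is largely about differences between activity types. A reader might infer that the sponsor intends a causal claim; the documents do not state one. What remains is that calling the group a control, beside stated aims about impact, invites that reading, and nothing in the plan rules it out.

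**Loneliness and belonging may have another analysis.** A reader might infer that the t-test is the only analysis of these two outcomes. The documents do not support that. The objectives say the activity component is meant to capture wellbeing before and after activities, and the change-score ANOVA is not restricted to mood. Equally, no text says these two scales are taken at both times. The point is unresolved.

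**Selection is not documented.** This stands. How people enter each component is not in the text available, and the eligibility criteria are the same for both. Shared criteria limit differences in walking ability but not in willingness to attend.

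**The coverage figures rest on chosen biases.** They do, and they are illustrations only. Nor does any text propose entering several scores per person as independent records; the expected 27 per group points to one value each.

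**Control and single cohort need not contradict each other.** Accepted: a non-randomised comparison group can be a cohort. The two labels should still be aligned.

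**It is a pilot.** That excuses a feasibility-based sample size. It does not make the contrast answer a question about activity effects.

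**Conclusion.** The concern holds in a conditional form. If the survey-only group serves as a control, as Study Design names it, the unadjusted contrast cannot separate an activity effect from who attends or from survey setting, and the plan leaves open which activity score is meant. The interval is about ±0.55 SD at 27 v 27. The bias has unknown size and direction; coverage of 89%, 81% and 56% applies only under assumed prior differences of 0.2, 0.3 and 0.5 SD.

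A reader might also infer that within-person pre/post change would isolate the activity effect. It would not. The plan has no period without an activity, so the change removes between-group selection but leaves the effects of repeat completion, expectancy and the outing itself.

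This should be changed, because it alters what the trial can conclude. Confidence is medium, since the content of the surveys and the route into each component are not in the text available.

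**What to change.** 1. **Statistical Considerations, question 4.** Enter one score per activity participant: the first pre-activity score, taken before any session. Suggested text:

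> The mean difference between the survey-only score and the first pre-activity score, with its 95% CI, describes how the two samples differ at entry. It is not an estimate of an activity effect.

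   Report the IPAQ in the same descriptive way. An IPAQ-adjusted estimate is optional; it would not remove selection on willingness to attend. Note that the arrival survey is still completed on site, so a setting difference remains.

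2. **Study Design, question 1.** Stop calling the survey-only group a control for the activity sessions, in line with question 2.

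3. **Time points.** State when each scale is taken. Take loneliness and belonging before and after each session, and base conclusions on within-person change and its comparison between activities. State that, with no period without an activity, this change does not exclude repeat-completion, expectancy or outing effects. If the scales are not taken at both times, state that the design does not estimate an activity effect on these two outcomes.

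**Cost.** Wording in two sections, and no extra participants or visits. If the scales are not already in the session surveys, each survey gains at most 3 + 12 = 15 items, or 15 × 6 = 90 item responses per participant over three sessions. The between-group contrast would no longer carry any activity effect, so the sponsor gives up a reading that the design could not support.
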